5.2 FOLLOW UP ASSESSMENTS

Phone assessments will be permitted for 6 month assessments, as a last resort, for participants who are unable to come in-person. The 1 month assessment will take about 45 minutes, the final assessment at 6 months will take about 60 min.

Administered Assessment	Baseline	1-Month	6-Month
Demographics	X		
ART Use and Adherence	X	X	X
HIV Sex Risk Behaviors	X	X	X
HIV Risk Categories	X		
HIV Disclosure	X		X
HIV Stigma	X	X	X
Substance Use Stigma	X	X	X
Substance Use Daily Life Experience (SRS)	X		
Acceptance and Action (AAQ-II – SA)	X	X	X
Patient Health Questionnaire (PHQ-9)	X	X	X
Anxiety (GAD-7)	X	X	X
Partner Violence and Sexual Assault	X		
Alcohol Use: AUDIT-C	X		
Perceived Alcohol Stigma	X		
Drug Use	X	X	X
Overdose	X		X
Social Support Scale	X		X
VR-12 Health Survey	X		X
Health Care Utilization	X		X
Abbreviated PTSD Checklist	X		
Involvement with Police	X		X
[‡] Satisfaction with the Intervention		X	
*HIV Testing History	X		
^a COVID-19 testing history, risk behaviors, and perceptions			X

[‡]Intervention group participants only

*If this information is not collected at baseline, RAs will collect this information at a later study visit.

^a Not administered to all 6-month participants

6. PARTICIPANT SAFETY

Boston Medical Center, First St. Petersburg Pavlov State Medical University/Global Health Institute and their Institutional Review Boards (IRB), the Principal Investigator ([name]) and the site PI and project manager are responsible for monitoring the pilot RCT proposed for the R00 phase and for ensuring the safety of participants. As the research is conducted in Russia, [name] will verify at each weekly conference call meeting if any adverse events or unanticipated problems occurred. The Russian investigators will notify the PI by email of serious incidents the same day. Discussion will take place on whether or not the incident meets the definition of an Unanticipated Problem (UP): is unexpected, possibly related to being in the research, and places subjects or others at greater risk of harm. Discussion will also take include if protocols or consents need to be modified, and if/when the incident should be reported to the IRBs. The principal risk of the study is breach of confidentiality. The remaining risks are minimal.

Participation in this study presents “minimal risk” which is defined as “the probability and magnitude of harm or discomfort anticipated in the research are not greater in and of themselves from those ordinarily encountered in daily life or during the performance of routine physical or psychological examinations or tests,” (from 45 CFR 46.102(i)). The primary risk of the study is the risk of loss of confidentiality. This risk and

any other risk of study participation are addressed above and within Protection of Human Subjects. The risk of breach of confidentiality is best addressed by appropriate study procedures; however, the PI will be responsible for assuring that study procedures are adhered to regarding data security, data transfer, and communications in tracking participants by meeting regularly with study staff, reviewing procedures, and performing quality control reviews of study forms as described above.

6.1. SPECIFICATION OF SAFETY PARAMETERS

An **Adverse Event (AE)** is defined as any abnormal or harmful behaviors, increasing severity of symptoms that are identified by the interventionist, suicidal behaviors or attempts, breach in the protection of participant data or breach of confidentiality whether or not considered related to the subject's participation in the research.

Stable chronic conditions that were present prior to study entry and do not worsen are not considered AEs.

SERIOUS Adverse Event (SAE) – is any adverse event that

- (1) results in death;
- (2) is life-threatening;
- (3) results in inpatient hospitalization or prolongation of existing hospitalization;
- (4) results in a persistent or significant disability/incapacity;
- (5) results in a congenital anomaly/birth defect; or
- (6) based upon appropriate medical judgment, may jeopardize the subject's health and may require medical or surgical intervention to prevent one of the other outcomes listed in this definition (examples of such events include allergic bronchospasm requiring intensive treatment in the emergency room or at home, blood dyscrasias or convulsions that do not result in inpatient hospitalization, or the development of drug dependency or drug abuse).

Life-threatening means that the event places the subject at immediate risk of death from the event as it occurred.

Unanticipated Problem (UP) – is defined as an event, experience or outcome that meets all three of the following criteria:

- is unexpected; AND
- is related or possibly related to participation in the research; AND
- suggests that the research places subjects or others at a greater risk of harm (including physical, psychological, economic, or social harm) than was previously known or recognized.

Possibly related means there is a reasonable possibility that the incident, experience, or outcome may have been caused by the procedures involved in the research

Unexpected means the nature, severity, or frequency of the event is not consistent with either:

- the known or foreseeable risk of adverse events associated with the procedures involved in the research that are described in (a) the protocol-related documents, such as the IRB-approved research protocol, any applicable investigator brochure, and the current IRB-approved informed consent

- document, and (b) other relevant sources of information, such as product labeling and package inserts; or
- the expected natural progression of any underlying disease, disorder, or condition of the subject(s) experiencing the adverse event and the subject's predisposing risk factor profile for the adverse event.

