2.7 INCLUSION CRITERIA

To be eligible to participate in the trial, participants will need to meet the following inclusion criteria:

1. 18 years old or older
2. HIV-positive
3. Current injection drug use (past 30 days)
4. Not currently on ART
5. Provision of contact information for two contacts to assist with follow-up
6. Address within 100 kilometers of St. Petersburg
7. Not enrolled in any other research studies
8. Possession of a telephone (home or cell)
9. Able and willing to comply with all study protocols and procedures over 6 months
10. Available at the specific days of the week and times that the group sessions will be occurring for the subsequent 3-4 weeks (to ensure that participants randomized into the intervention arm will be able to receive the intervention)

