5. ASSESSMENTS

5.1 BASELINE ASSESSMENT

The baseline assessment will be conducted immediately following the screening and informed consent. The assessment will be interviewer-administered.

Participants will be assessed as part of this study using validated interview instruments covering the following topics, which will take approximately 60 min:

- Demographics, modified from the ASI Lite-CF Clinical/Training Version and Addiction Severity Index⁷
- ART Medication Use and Adherence
- HIV Sex Risk Behaviors, questions are adapted from the Women's Health Coop Baseline Questionnaire
- HIV Risk Categories, using questions adapted from the American Red Cross and Navaline et al.¹⁷
- HIV Disclosure, using questions from Stein et al. (1998)¹⁸ and Raj et al. (2006)¹⁹
- HIV Stigma, using the Berger et al. HIV stigma scale²⁰ and Leickness et al.
- Substance Use Stigma^{21, 22}, via a modified Substance Abuse Self-Stigma Scale
- Substance Use enacted interpersonal stigma, through the Stigma-Related Rejection Scale (SRS)
- Psychological flexibility, by the Acceptance and Action Questionnaire – Substance Abuse (AAQ-SA)
- Mental health through the Patient Health Questionnaire (PHQ-9)
- Anxiety by the GAD-7
- Partner Violence and Sexual Assault, adapted from the TAJ assessment
- Alcohol Use, via the AUDIT-C²⁸
- Perceived alcohol stigma, using questions from Luoma et al. (2010)
- Drug use by an adapted version of the Risk Behavior Survey^{30, 31}
- Overdose and Suicide, using adapted questions from Britton et al. (2012)³⁴
- Social Support, using the harmonized STTR document^{35, 36}
- VR-12 Health Survey & MOS-HIV^{37, 38}
- Care utilization
- Post-Traumatic Stress Disorder via the Abbreviated PTSD Checklist
- Police involvement
- HIV Testing History

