The DSMB meets by conference call at a minimum of every 6 months. The Board is charged with evaluating the quality of trial administration, monitoring safety issues, and providing guidance on scientific, methodological and ethical issues. Specifically, the Board reviews investigators' plans and processes for

identifying individual or patterns of adverse events and review accumulating safety data. Following each meeting, the DSMB will make recommendations on modification, or termination of the study.

The Board will be composed of three full members (inclusive of the DSMB Chair) and 1 adjunct member.

Full Members of the DSMB are:

1. [name] (Professor of Epidemiology and Biostatistics, BUSPH), Chair of DSMB
2. [name] (Professor of Medicine, Brown Medical School)
3. [name] (Associate Professor of Psychology, Indiana University-Purdue University Indianapolis)

Consulting with the DSMB as needed for this trial will be valuable for further ensuring the quality and scientific validity of the study. An agenda will be provided detailing the studies to be discussed. If any issues arise with the R00 SCRIPT study, it will be added to the agenda. It is estimated that the meeting will be scheduled for 1.5 hours. Communication in the interim will be as needed. Unscheduled meetings can be requested by any party with the responsibility of overseeing the study. Requests can be made to the DSMB Chair, PIs, or NIAAA officials. The Chair, in collaboration with the URBAN ARCH Administrative Coordinating Core or NIAAA, will schedule any unplanned meetings.

The Methods and Time for Assessing, Recording, and Analyzing Safety Parameters

All AEs will be assessed to determine if they meet criteria for a Serious Adverse Event (SAE). All AEs will be reported to [name] at weekly phone meetings. [name] will be designated to distinguish a serious adverse event (SAE) from a non-serious adverse event. The site PI and project manager (both MDs) will monitor SAE and AE on site. If the AE is serious, then the SAE form must be completed and appropriate reporting measures followed. Investigators are encouraged to consult with the PI, if they are uncertain how to classify an event.

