To summarize: upon determining an Adverse Event is Serious, the following procedures should be followed:

- The study staff, while meeting/talking with the participant or person providing details on the event, will gather as much information about the event from the participant as possible and complete the appropriate forms.
- The completed AE and SAE forms will be reviewed by key personnel on the Pavlov team. Any relevant clinical documents (labs, physician notes) available at that time will be provided to key personnel on the Pavlov team within 24 hours of finding out about the event.
- After initial notification, the SAE must be updated with any additional information.

All unanticipated problems must be reported to the US team immediately.

Reporting Procedures to the IRB and NIDA

Each site will follow reporting guidelines set forth by their Institutional Review Boards regarding unanticipated problems, adverse events, and serious adverse events. Deaths and serious breaches of confidentiality reported to research staff will be reviewed by the site PI and reported to the PI the same day, who will then report to the IRB. The co-investigators and PI will review aggregate data every 6 months. Should any irregularities arise, the PI will consult with the DSMB, as described above. According to the minimum standards for AE and SAE reporting to NIDA, we will report AEs and SAEs once per year through the annual progress report.

Reporting mechanisms of IRB actions to NIDA: The PI will provide a summary of safety-relevant events to NIDA on an annual basis as part of the progress report.

Report of changes or amendments to the protocol. All changes or amendments to the protocol will be submitted to both IRBs prior to changing study procedures.

BUMC Reporting Guidelines:

The Principal Investigator at BMC/BU Medical Campus will report Unanticipated Problems and Adverse Events to the BMC/BU Medical Center IRB in accordance with IRB policies:

- Unanticipated Problems involving a fatal or life-threatening event will be reported to the IRB within 2 days of the investigator learning of the event.
- Unanticipated Problems not involving a fatal or life-threatening event will be reported to the IRB within 7 days of the investigator learning of the event.

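### The adverse event list in Section 6.1 does not clearly cover medical admissions, medical deaths or accidental overdoses, conflicts with the section's own SAE text, and relies in part on staff whom only one arm meets

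*Combined protocol and SAP*

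**What the plan says.** Section 6.1 lists what counts as an AE: "any abnormal or harmful behaviors, increasing severity of symptoms that are identified by the interventionist, suicidal behaviors or attempts", and breaches affecting participant data or confidentiality, all irrespective of relatedness. There is no catch-all for other untoward events.

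The section then says that an SAE "is any adverse event that" meets one of six criteria. These include death and an event that "results in inpatient hospitalization or prolongation of existing hospitalization". The sixth criterion is illustrated with bodily illnesses: bronchospasm, blood dyscrasias and convulsions. One exemption is stated: "Stable chronic conditions that were present prior to study entry and do not worsen are not considered AEs".

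Section 6.2 keeps the same order: AEs are screened for seriousness, and nothing else is. It also foresees AEs that are fatal. Under the IRB and NIDA reporting heading it adds a separate route: "Deaths and serious breaches of confidentiality reported to research staff" go to the site PI, to the PI the same day, and then to the IRB. Section 6 adds same-day notice to the PI of serious incidents, a term it does not define.

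**The concern.** Participants are HIV-positive, not on ART at entry and injecting within the past 30 days (Section 2.7). Overdose, infection and admission are foreseeable during six months. A reader applying the list as written has no item under which to enter a pneumonia admission or an injury, and seriousness is never assessed for an event that was not first called an AE.

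The symptom item adds an imbalance between arms, because it turns on what the interventionist sees. The behaviour item has the opposite fault: taken literally, it includes the conduct that made the person eligible.

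At stake are the reports built on these categories: the AE summary to the Boston IRB at continuing review, with its statement on the overall pattern of events; the quarterly and expedited reports to the Pavlov IRB; and the reports to NIDA. Section 6.2 also says that the DSMB does not review unless issues arise, so an undercount makes that safeguard less likely to be used.

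**Working it through.** The plan gives no figure to reproduce. The check is to put typical events through the text.

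**Classification under Sections 6.1 and 6.2**

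- *Pneumonia admission or injury.* No list item names it. The bodily SAE examples imply that it can be an AE. Two staff members could reach opposite answers, each citing Section 6.1.
- *Admission for worsening HIV disease.* It is on the list only if the interventionist identifies worsening symptoms. The exemption for stable conditions implies that a worsening one is an AE whoever sees it.
- *Accidental overdose.* It is an AE if the injecting behind it is read as a harmful behaviour, and then an SAE if it is fatal, is life-threatening or leads to admission. On a narrower reading it is not listed.
- *Medical death.* It is not plainly on the list, so SAE status is open, but the death route carries it to the PI and the IRB.
- *Continued injecting at the entry pattern.* It is an AE on a literal reading. The only exemption is for chronic conditions; none covers baseline behaviour.
- *Suicide attempt or confidentiality breach.* Both are clearly covered.

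**Reach of the symptom item**

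Inputs: 65 intervention and 35 control participants, with only the intervention group meeting the interventionist (Section 2.4). Target days (Section 3.5.A): session 1 at day 7 and session 3 at day 21 after baseline; the intervention arm's 6-month visit 180 days after session 1.

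- Control arm: 0 of 35 participants can trigger the item.
- Intervention arm: target day of the 6-month visit = 7 + 180 = 187. Days after session 3 = 187 − 21 = 166. Share = 166 / 187 = 0.89.

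The windows allow later sessions (session 3 closes at day 36) and are described as guides, so 89% is the on-target figure.

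**Do other data sources close the gap?**

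The Section 5.2 table asks both arms about overdose and health care use at baseline and 6 months, but not at 1 month. Nothing links those answers to AE or SAE forms. Such a link is feasible: the suicide safety protocol in Section 6.2 already ties a PHQ-9 answer to a defined action.

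The control schedule in Section 3.5 shows no AE rows, while the intervention schedule does. I give this little weight, because the table may have been damaged in extraction.

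**The case against.** A reader might infer that medical admissions, deaths and overdoses cannot become SAEs in either arm. The documents do not support that. The exemption limited to stable conditions, the bodily SAE examples and the mention of fatal AEs all suggest that medical events were meant to be included. An overdose can be read as a harmful behaviour. Worsening that the interventionist sees in the intervention arm can become an SAE on admission. This is an internal contradiction, not a clean exclusion.

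Nor can the behaviour item be called too wide and too narrow at once for the same injection-related event. If injecting counts, its serious consequences count too. What stands is that the text does not say which reading applies, and neither reading reaches an admission unrelated to drug use unless one of the other items applies.

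The other routes matter as well. Deaths of any cause and in either arm reach the IRB once staff learn of them. The Unanticipated Problem definition does not require an AE, so unexpected, possibly related harm is reportable in any case. It would therefore be too much to say that the IRB pattern statement could not be supported. These routes leave out non-fatal events judged expected or unrelated, and they do not settle SAE status.

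Finally, this is a declared minimal-risk behavioural trial with no safety outcome in Sections 2.1 or 8, and a tailored AE list is a legitimate choice. Section 9.1 also mentions established protocols for identifying AEs, which are not reproduced. Both points lower the stakes; neither reconciles Section 6.1 with itself.

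**Conclusion.** The concern holds as an inconsistency with a practical consequence. The AE list does not clearly cover medical admissions, medical deaths or accidental overdoses, and it conflicts with SAE text in the same section. Such events may be missed or classified inconsistently. Ascertainment can differ between arms, because the symptom item is closed to the 35 control participants and has little scope for about 89% of target follow-up in the other 65. The gap lies mainly in non-fatal medical events and in SAE labelling.

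The number of affected events cannot be derived from the documents. For scale only, and as assumptions: if 5% to 20% of participants were admitted within six months, that is 100 × 0.05 = 5 to 100 × 0.20 = 20 people. At 1 to 5 deaths per 100 person-years over 100 × 0.5 = 50 person-years, 0.5 to 2.5 deaths would be expected. A reader might go on to infer that most of these would fall outside the AE definition. Nothing in the documents shows what share would, and the verdict does not depend on these rates.

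The planned efficacy comparisons are unaffected. The change is worth making because safety reporting rests on these categories and the repair is small.

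**What to change.** Reconcile the opening definition in Section 6.1 with the SAE criteria:

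- Define an AE as any untoward medical, psychological or social occurrence in an enrolled participant of either arm up to the 6-month visit, whoever identifies it and whether or not it is related. Keep the data and confidentiality breach items.
- State that drug use at the participant's baseline pattern is not in itself an AE.
- Add a reconciliation rule for both arms: 6-month overdose answers, and health-care-use answers where they record an admission, are checked against AE/SAE forms.

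The rule should not rely on a 6-month suicide-attempt item. Section 5.1 lists "Overdose and Suicide" at baseline, but the 6-month row in Section 5.2 names only overdose. Nor do the documents show whether the health-care-use questions record admissions, so that part is conditional.

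The cost is one protocol paragraph, submitted to both IRBs as an amendment, and one data check on items already collected. The downside is more SAE forms and a higher reported count, mostly for background events.

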2.4 STUDY DESIGN

SCRIPT is a Randomized Controlled Trial (RCT) among 100 HIV+ PWID, which aims to test the feasibility of the SCRIPT intervention and evaluate its effectiveness on the reduction of internalized stigma as well as self-reported entry into substance abuse treatment or initiation of ART. Eligible participants will be randomly assigned into one of two groups: 1) Control group receiving CSO site standard of care or; 2) ACT intervention. Both the intervention group and the control group will receive standard of care counseling and referral to addiction treatment and HIV treatment at the CSO sites. Following their baseline assessment, participants assigned to the intervention group will meet with the interventionist three times over one month in approximately 13 groups of 5 people each. All three sessions will be in groups, except for the occasional individual make-up 2nd session (more details in section 3.6B). Study outcomes will be assessed at 1 and 6 months (Figure 1).

Figure 1 illustrates the design of this 2-arm RCT with 65 participants in the SCRIPT intervention arm and 35 participants in the standard of care arm.

Figure: SCRIPT Study Design

Throughout the course of the study, participants in both groups will be expected to participate in three in-person assessments (baseline, 1 month and 6 months).

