3.4 CONTROL GROUP

Participants in the control group will receive standard care as normally provided to patients by civil society organizations. This could include information on HIV and substance use disorders, counseling, referral to addiction treatment clinics, and referral to HIV treatment clinics. They might also be given printed information, including phone numbers, on places that provide HIV medical care and substance use treatment.

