3.5 SCHEDULE OF DATA COLLECTION

		Phone Screener	Screener and Baseline		ACT Sessions 1-3	1-month assessment (4 weeks)	6 month visit (24 weeks)
			In-person Screener	Baseline			
Screening	Verification of HIV and hx of IDU	X	X				
	Screening Questions	X	X				
Enrollment	Sign Informed Consent		X				
	Complete contact information/verify numbers			X			
Assessment	Baseline Study Assessment			X			
	1-Month Study Assessment incl ACT satisfaction questions					X	
	6-Month Study Assessment						X
	Interventionist Checklist				X		
Randomization	Randomization			X			
Intervention	Adverse Events			X		X	
	ACT Intervention				X		
Other	Compensate for Participation			X	X	X	X
	Provide Resource Card			X			
	Report Adverse Events			X	X	X	X
	Complete Tracking Forms		X	X	X	X	X

Control Group						
		Phone Screener	Screener and Baseline Visit		1 mo (4 weeks)	6 mo (24 weeks)
			In-person Screener	Baseline		
Screening	Verification of HIV and substance use	X	X			
	Screening Questions	X	X			
Enrollment	Sign Informed Consent		X			
	Complete contact information/verify numbers			X		
Assessment	Baseline Study Assessment				X	
	1-Month Study Assessment					X
	6-Month Study Assessment					X
	Randomization				X	
Other	Provide Resource Card				X	
	Compensate for Participation				X	X

	Complete Tracking Forms			X	X	X
--	-------------------------	--	--	---	---	---

3.5.A. VISIT WINDOWS

ACT Intervention Session Windows for Intervention Group

1st ACT Session

- Window open: 1 day post baseline
- Target date: 7 days post baseline
- Window close: 31 days post baseline
- Window length: 30 days

2nd ACT Session

- Window open: 8 days post baseline
- Target date: 14 days post baseline
- Window close: 29 days post baseline
- Window length: 21 days

3rd ACT Session:

- Window open: 15 days post baseline
- Target date: 21 days post baseline
- Window close: 36 days post baseline
- Window length: 21 days

Research Assessment Windows for Intervention and Control Group

Intervention Group 1 Month (4-week) Visit

- Window open: 16 days post first group session
- Target date: 30 days post first group session
- Window close: 90 days post first group session
- Window length: 74 days

Intervention Group 6 Month (24-week) Visit

- Window open: 151 days post first group session
- Target date: 180 days post first group session
- Window close: 240 days post first group session
- Window length: 89 days

Control Group 1 Month (4-week) Visit

- Window open: 16 days post baseline

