- Adverse Events (including Serious Adverse Events) will be reported in summary at the time of continuing review, along with a statement that the pattern of adverse events, in total, does not suggest that the research places subjects or others at a greater risk of harm than was previously known.

Pavlov Reporting Guidelines:

What Event is Reported	When is Event Reported
Fatal or life-threatening unexpected, suspected serious adverse reactions	Within 7 calendar days of initial receipt of information
Non-fatal, non-life-threatening unexpected, suspected serious adverse reactions	Within 15 calendar days of initial receipt of information
AEs and UPs	On a quarterly basis

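### Adverse-event reporting is scheduled only for the ACT arm, and one element of the definition depends on the interventionist, so control-arm events are likely to be recorded less completely

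*Combined protocol and SAP*

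**What the plan says.** **Definition.** Section 6.1 lists several kinds of adverse event. One is "increasing severity of symptoms that are identified by the interventionist". Others carry no such condition: abnormal or harmful behaviour, and "suicidal behaviors or attempts, breach in the protection of participant data or breach of confidentiality". A serious adverse event (SAE) is then defined as an AE that meets a seriousness criterion.

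**Who meets an interventionist.** Under section 2.4, "participants assigned to the intervention group will meet with the interventionist three times over one month". Section 3.4 says "Participants in the control group will receive standard care as normally provided to patients by civil society organizations" and describes no contact with an interventionist.

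**Schedule.** Section 3.5 has one table per arm. The ACT table has a row headed Adverse Events, marked in two columns, and a row "Report Adverse Events", marked at baseline, the ACT sessions, 1 month and 6 months. The table headed "Control Group" repeats the neighbouring rows for the resource card, compensation and tracking forms but shows neither AE row.

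**Shared visits.** Section 2.4 states that "participants in both groups will be expected to participate in three in-person assessments (baseline, 1 month and 6 months").

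**Use of the data.** Under section 6.2 the investigators review aggregate data every 6 months and turn to the DSMB if something irregular appears. At continuing review the Boston IRB receives the AEs in summary form, "along with a statement that the pattern of adverse events, in total, does not suggest that the research places subjects or others at a greater" (the comparison is with the risk known before).

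**The concern.** Followed as written, these rules make the recording of AEs depend on the arm. ACT participants have reporting points that controls lack, and one kind of event is tied to a member of staff whom controls are not due to see.

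The people enrolled inject drugs, have HIV and are not on ART, so some worsening is to be expected in either arm. Section 6.1 judges whether an event is unexpected partly by its frequency against the natural course of the participant's condition. The concurrent control arm is the obvious yardstick for that. If its events are recorded less completely, an apparent excess under ACT could reflect closer observation rather than harm, and the yardstick is weak for the judgement the investigators must give the IRB.

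**Working it through.** The documents give no AE rate, no detection rate and no safety sample size, so there is no figure to reproduce. The check is a comparison of texts and a count.

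1. **Scheduled AE-reporting points, ACT arm (section 3.5).** Baseline 1 + sessions 3 + 1 month 1 + 6 months 1 = 6.

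2. **Remove baseline.** Sections 3.1 and 4.5 place the baseline assessment before randomization, so AE capture there cannot yet differ by arm. After randomization the ACT count is 6 − 1 = 5, at most, since it assumes that all sessions and visits are attended.

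3. **Control arm.** The table as extracted shows 0. With the arm sizes in section 2.4, the totals are 5 × 65 = 325 scheduled points against 0 × 35 = 0.

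4. **Does other text supply the missing enquiry?**
   - Section 4.5 lists the tasks at the 1- and 6-month visits for both arms: contact details, questionnaire, compensation and scheduling. There is no AE enquiry.
   - The assessment table in section 5.2 has no AE item.
   - The form table in section 7.3 has an SAE form, used as needed, and no AE form tied to a visit.

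5. **Routes that reach both arms.**
   - Section 6.2: the suicide protocol runs from PHQ-9 item 9 or spontaneous disclosure, to an assessor or an interventionist.
   - Section 6.2: events discovered between visits are to be recorded.
   - Section 6: AEs are checked at the weekly call.
   - Section 9.1: staff are trained to assess for AEs.
   - Section 5.2: PHQ-9, GAD-7 and drug use are collected in both arms at all three visits; overdose and health care use at baseline and 6 months.

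   Of the AE-recording routes, only the suicide item is a scheduled question. The others need someone to volunteer or notice an event.

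6. **The definition.** The interventionist condition applies to one element only. Read literally, worsening seen only by a research assessor falls outside that element. That covers controls throughout and ACT participants after their last session. The SAE definition inherits the wording. It also sits awkwardly with section 6.2, where assessors decide the action for mild and moderate AEs, and with section 9.1. These places need to be reconciled.

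7. **Direction and size.** If a share *s* of true events is recorded in each arm, then

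   apparent risk ratio = true risk ratio × (s_ACT ÷ s_control).

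   With s_control below s_ACT, the apparent ratio is too high, to ACT's disadvantage. Neither share is stated or derivable, so the size of the bias cannot be calculated.

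8. **After the fix.** At the shared visits after randomization, each participant would have 2 points in either arm: 2 × 65 = 130 for ACT and 2 × 35 = 70 for control. The 3 × 65 = 195 session contacts would remain specific to ACT.

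**The case against.** The strongest reply has four parts.

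- **Neutral routes exist.** Those in step 5 of the working carry no restriction by arm, and the same assessors see everyone. This stands. A reader might infer that control-arm AEs are not captured, or that real harm could never be told from background. The documents support neither reading: symptoms and drug use are measured equally in both arms, even where a change is not logged as an AE.
- **The table is weak evidence.** The control table is visibly damaged, with shifted marks and its last row split off, so a lost row cannot be ruled out. This stands as a caution. Against it, both AE rows would have to be missing, and the wording of section 6.1 is running text, unaffected by the table. That wording supports only the definitional half of the point, however; the count of 5 against 0 rests on the table.
- **A reporting row may not mean active questioning.** Section 4.5 lists no AE enquiry for either arm, and the extra contact in group sessions is inherent in the comparison. Both are true. They are reasons to state the same enquiry for both arms and to keep session-detected events apart, not reasons to leave the schedules unequal.
- **No by-arm AE analysis is planned.** Section 8 has none, the periodic review is of aggregate data, the IRB statement concerns the total pattern, and unanticipated problems are judged event by event. This stands and limits the consequence. Any bias would also overstate ACT's harms rather than hide them.

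**Conclusion.** The point holds in a limited form. As written, scheduled AE reporting after randomization is up to five points per ACT participant and none per control, and the symptom-worsening element of the definition depends on someone controls are not scheduled to meet. Recording is therefore likely to be less complete in the control arm. That is under-ascertainment, not absence.

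A reader might want to attach a spurious risk ratio by assuming detection rates. The documents give none, so any such figure would only restate the assumption.

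The consequence is confined to safety: a by-arm AE summary would tend to disfavour ACT, and the control arm is a poor benchmark for the AE pattern. The primary outcomes are unaffected. The plan should be changed, but the matter is not critical in a trial described as minimal risk. The conclusion assumes that the extracted control table is complete in this respect, which the sponsor can settle from the source table, and that staff follow the schedule and definition as written.

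**What to change.** 1. **Schedule (section 3.5).** Add the same AE reporting row to the control table at the existing baseline, 1-month and 6-month visits. Have the assessor use one question and one form in both arms, and add the task to the visit list in section 4.5.
2. **Definition (section 6.1).** Extend the symptom-worsening element so that identification by the interventionist or by any other member of study staff counts. This also brings it into line with sections 6.2 and 9.1.
3. **Any summary by arm.** Compare only events elicited at the shared visits after randomization (1 and 6 months). List events noted only in ACT sessions separately.

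The cost is one short form at control visits that already take place, and a few changed sentences. No extra visits or staff are needed. The downside is a few more events to process.
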